6.2 Schedule of Activities: Study Drug Infusion Detail

	Dose 1			Doses 2-5 ⁵			
Procedure	Pre	During	Post	Pre	During	Post	
Study Drug Administration ¹⁶		Х			Х		
AE Assessment	Х			X			
Con Med Assessment	Х			X			

¹ **tPA or Mechanical Thrombectomy:** Subjects will be eligible to consent for this study following initiation of tPA administration or the decision to begin mechanical thrombectomy, whichever occurs sooner.

- ² Informed consent: Informed consent (and re-consent, as applicable) must be obtained by the CSS PI or a qualified designee (licensed physician investigator) listed on the FDA Form 1572. If informed consent was originally provided by a legally authorized representative, and, in the opinion of the CSS PI, the subject's mental status improves sufficiently to enable him/her to provide informed consent, the subject must be re-consented in person at the current or next study visit. Re-consenting once the subject regains capacity is an expected part of Good Clinical Practice (GCP)
- ³ Weight: Every effort should be made to obtain an actual pre-dose weight for each subject, as all investigational doses will be based on this weight. If a subject's weight was estimated for the purposes of study drug dose calculation, then an actual weight must be obtained within 24 hours of dose 1. For those sites participating in the PK study, an actual weight must also be recorded on the day of PK sampling.
- ⁴ Acute Blood Pressure Monitoring: SOC tPA blood pressure monitoring requires that for the first 24 hours after starting treatment, collection is: every 15 minutes for 2 hours after starting the infusion, then every 30 minutes for 6 hours, then every hour for 18 hours. The eCRF will capture one hourly time point for the first 24 hours. For subjects who undergo mechanical thrombectomy only, one hourly time point for the first 24 hours must be captured.
- ⁵ Day 3: If a subject is discharged prior to receiving all 5 doses of study drug, then further dosing will be halted and the subject should be seen for Day 7 assessments.
- ⁶ Vital Signs: Heart rate, respiratory rate, blood pressure, oxygen saturation and temperature should be collected daily during the first 6 days (SOC). In addition, following each 3K3A-APC infusion, vital signs should be collected just prior to and at end of infusion (EOI) and every hour for 4 hours (+/- 30 minutes). Temperature at EOI is not required.
- ⁷NIHSS: A NIHSS should be collected daily, or more frequently when clinically indicated.
- ⁸ Brain Imaging: As per local standard of care, CT or T1 MRI must be performed at baseline and 24-36 hours following tPA bolus administration. Note that MRI may be used in place of CT for the baseline scan only if the site receives prior approval from the CCC.
- ⁹ Chemistry: Perform liver function, glucose and electrolytes.
- ¹⁰ **CBC:** Perform a complete blood count with platelets; a differential must be performed if the white blood cell count is elevated (above the site's ULN).
- ¹¹ Coagulation: Perform aPTT, PT, INR and fibrinogen. For each 3K3A-APC dose, samples should be drawn and processed pre-dose (window varies; see below) and 1 hour post-dose (+/- 15 minutes). For doses 2-5 the pre-dose window is within 60 minutes prior to the start of the infusion. For dose 1 however, note that some of these pre-dose assessments are required for screening and they should all be prior to tPA (in those subjects who receive tPA). Therefore, the pre-dose draw for dose 1 may be more than 60 minutes prior to the infusion. If the pre-dose samples for dose 1 are drawn after tPA they should not be drawn until at least 20 minutes has passed since tPA finished so as to minimize tPA's effect on the laboratory results.

¹² Urinalysis: Microscopic urinalysis must be performed if dipstick is positive for RBCs.

- ¹³ Pregnancy Test: Serum or urine pregnancy test for women of child-bearing potential only.
- ¹⁴ ECG: One post-dose ECG should be collected at 'end of infusion' (Cmax) (+ 5 minutes). The Investigator can decide which dose, 1-5, will be used for ECG collection.
- ¹⁵ PK Samples: PK samples will be collected from subjects at a subset of participating sites; samples will be collected following one of the doses of 3K3A-APC at the following time points: end of infusion, 20, 40, 60 and 80 minutes post-dose. The Investigator can decide which dose, 2-5, will be used for PK collection.
- ¹⁶ Study Drug Administration: 3K3A-APC (or placebo) will be administered as a 15-minute infusion every 12 hours for 5 doses, or until discharge. The first dose of study drug (or placebo) should be started 30 to 120 minutes following completion of tPA or initiation of mechanical thrombectomy (arterial puncture), whichever occurs sooner. Subsequent doses should be given every 12 hours (+/- 1 hour) for 5 total doses (or until discharge). Dose 1 must be confirmed in the data system within 2 hours of infusion time.

6.3 Timing of Study Activities

6.3.1 Screening/Pre-Randomization Evaluations/procedures

Screening procedures are described in Section 4.4.

6.3.1.1.1 Admission/Standard of Care Procedures

The following procedures will be performed upon arrival of the stroke team (those marked with an asterisk* will be collected in accordance with standard of care and are expected to be performed prior to tPA, mechanical thrombectomy and informed consent):

- Medical history and PE*
- Assessment of Baseline Medications (all medications taken within 3 days prior to tPA administration)*
- Vital signs (blood pressure, heart rate, temperature, respiratory rate, oxygen saturation)*
- Body weight*
- Non-contrast enhanced head CT* or MRI (if preapproved)
- Neurological examination: NIHSS*
- 12-lead electrocardiogram (ECG)*

Laboratory Tests:

- CBC (complete blood count and platelets)*
- Chemistries (liver function, glucose and electrolytes)*
- Coagulation (PT, aPTT, INR, fibrinogen)*
- Urinalysis (dipstick or microscopic, per SOC)*

Patients who meet the criteria for tPA administration or mechanical thrombectomy or both (see Section 5.5.1) will be considered for participation in this protocol. The administration of tPA should follow the American Heart Association's national accepted published guidelines¹⁴. Use of mechanical thrombectomy should follow the local Institutional protocol, and should only include the use of FDA-approved thrombectomy devices. Note that MRI may be used in place of CT for standard of care imaging prior to tPA/mechanical thrombectomy only if the site receives prior approval from the CCC.

The AHA Guidelines recommend assessing PTT, INR, and fibrinogen prior to administering tPA¹⁴. Eligibility for enrollment in this study is based on PTT and INR levels. So as to have an accurate reflection of the subject's true baseline, the pre-dose 1 blood draws for coagulation assessments should occur as SOC prior to tPA for patients receiving tPA. If that is not done for some reason, then the pre-dose 1 blood draw should occur at least 20 minutes after tPA completion, in order to minimize tPA's effect on the levels.

6.3.1.2 Informed Consent

Once the patient begins tPA administration or the decision to begin mechanical thrombectomy is made, whichever occurs sooner, he/she can be presented with the consent form and evaluated for study enrollment. Refer to Section 4.4.3 for details on the consenting process.

6.3.1.3 Slot Assignment and Randomization

Following consent of the subject, or his/her legally authorized representative, the following assessments should be performed:

- Estimated pre-stroke mRS (to determine study eligibility)
- A pregnancy test in women of child bearing potential (serum or urine, per Investigator's discretion) will be required to qualify the eligibility of female patients.
- An actual pre-dose weight for each subject is preferred, as all investigational doses will be based on this weight. If a subject's weight was estimated for the purposes of study drug dose calculation, then an actual weight must be obtained within 24 hours of dose 1.

Subjects who have signed consent (or whose representatives have provided surrogate consent) and meet all inclusion and exclusion criteria can be randomized into the study; randomization will be managed electronically via the IWRS. The Investigator, or designee, should randomize the subject in the IWRS to receive the unique subject number, which will also be linked to the allocated treatment assignment (blinded to clinical staff). Subjects who will receive mechanical thrombectomy only should be randomized close to the start of the procedure (arterial puncture) to ensure that they continue to meet eligibility.

The unblinded pharmacist(s) will receive the treatment assignment from the IWRS that will be used to prepare the investigational treatment as described in Section 5.3.

It is important to confirm eligibility again close to investigational dose 1 as the NIHSS score may drop below 5 during the time between randomization and the first dose of study drug. For this reason, a repeat NIHSS should be assessed:

- Immediately prior to Dose 1 infusion if the subject received tPA treatment only, or
- Immediately prior to draping the subject in preparation for mechanical thrombectomy if the subject is to receive mechanical thrombectomy alone or in combination with tPA.

If the new NIHSS score has improved such that the subject is no longer eligible (repeat NIHSS<5) do not administer study drug. Submit the termination form and other required documents so that this subject can be replaced in the cohort. Refer to the NN104 'Manual of Operations' for more detail. Randomized subjects who experience significant neurologic improvement (defined as a NIHSS score <5) prior to receipt of study drug will be termed 'Early Responders' and will not be included in the study. 'Early Responders' will not be followed, and will be replaced in the CRM. Any subject who receives any amount of study drug will be considered "Dosed" and will be followed to the end of the study.

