4.4.4 Randomization/Treatment Assignment

Subjects will be randomized using an IWRS to either 3K3A-APC or placebo (in a 3:1 ratio). Twentytwo groups of four subjects are planned, but fewer may be enrolled should the study meet either of the early stopping criteria (see section 8.1.1). If at any time enrollment is so rapid that there are two consecutive cohorts in the DLT review period, subjects will be assigned to placebo until the earlier of the two cohorts has been reviewed. The additional placebo subjects will be closely monitored and their enrollment may be discontinued should the number enrolled exceed what was planned for the study.

The NeuroNEXT IWR system will also serve to inform the unblinded study pharmacist of the treatment assignment (refer to Section 5.3 for details on Study Drug Preparation).

Randomized subjects who do not go on to receive study treatment for any reason will not be included in the study and will be replaced if they were randomized to a cohort. For example, if a randomized subject experiences significant neurologic improvement (defined as a NIHSS score <5) prior to receipt of study drug he/she will be termed an 'Early Responder' and will not be included in the study. Any subject who receives any amount of study drug or placebo however, will be considered "Dosed" and will be followed to the end of the study.

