5.4 Administration of Study Drug

Study drug will be infused into a large bore peripheral arm vein at a rate of 400 mL/hr over 15 minutes for all dose levels. The first dose of study drug will be administered 30 to 120 minutes after tPA has completed or mechanical thrombectomy begins (arterial puncture), whichever is sooner. Subsequent doses of study drug should be given every 12 hours (+/- 1 hour) for 5 total doses (or until discharge, whichever occurs first). It is preferable not to skip doses of study drug, and should a dose need to occur outside of the +/- 1-hour window (which will be reported as a protocol deviation), doses should never be given within 8 hours of one another. Please note that PK samples should be drawn from the opposite arm. See 'Drug Storage, Handling and Administration Manual' for further instructions on administration.

After the study drug infusion is complete, the IV line should be flushed with at least 20 mL of normal saline to ensure complete administration of the residual study drug. The calendar date, 24-hour clock time of the beginning and end of the infusion, and the volume infused should be recorded for capture in the CRF.

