6.3.2.1.2 Study-Specific Post-Treatment Procedures

Investigational Dose #1:

The first investigational dose of study drug should be started 30 to 120 minutes following completion of tPA or initiation of mechanical thrombectomy (arterial puncture), whichever occurs sooner.

After administration of 100 mL of investigational treatment, the following should be performed:

• Vital signs (blood pressure, heart rate, temperature, respiratory rate, oxygen saturation) should be collected at end of infusion (EOI) and approximately every hour (+/- 30 minutes) for 4 hours, then per local SOC. Temperature at EOI is not required.

NOTE: the NINDS tPA protocol should guide vital sign collection following tPA administration; therefore, actual collection may be more frequent than what will be captured for this study protocol. The eCRF will capture one hourly time point for the first 24 hours. For subjects who undergo mechanical thrombectomy only, one hourly time point for the first 24 hours must be captured.

- Blood for coagulation (PT, aPTT, INR, fibrinogen) should be collected 1 hour after EOI (+/-15 minutes).
- One post-dose ECG should be collected at EOI (C_{max}) (+ 5 minutes). The Investigator can decide which dose, 1-5, can be used for ECG collection. Since the ECG collection is flexible, it should be planned well in advance so that it is collected as close to EOI as possible. Should the ECG window be missed, it is preferred to defer the collection to the next planned investigational dose.

Investigational Doses #2-5:

Subjects should receive 100 mL of investigational treatment every 12 hours (+/- 1 hour) for up to 5 total doses (refer to section 5.4). Subjects will only receive investigational treatment for as long as they remain as an inpatient. The following should be performed:

- Vital signs should be collected just prior to infusion, at EOI and approximately every hour (+/- 30 minutes) for 4 hours, then per local SOC
- Blood for coagulation (PT, aPTT, INR, fibrinogen) should be collected from the arm opposite the infusion:
 - Prior to each infusion (within 60 minutes of infusion)

- 1 hour after EOI (+/- 15 minutes)

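### In subjects who are to have both tPA and thrombectomy, the repeat eligibility NIHSS is timed to draping, so it can fall after Dose 1 and the rule against dosing at NIHSS below 5 cannot then operate

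*Protocol*

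**What the plan says.** Protocol 6.3.1.3 (Slot Assignment and Randomization) gives the purpose of the second NIHSS: "It is important to confirm eligibility again close to investigational dose 1". It then sets two times. For subjects treated with tPA alone, the examination is "Immediately prior to Dose 1 infusion if the subject received tPA treatment only". For anyone due to have thrombectomy, with or without tPA, it is "Immediately prior to draping the subject in preparation for mechanical thrombectomy". SAP section 4 repeats both rules.

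The same protocol section gives the consequence: "If the new NIHSS score has improved such that the subject is no longer eligible (repeat NIHSS<5) do not administer study drug". Protocol 4.4.4 says that a randomized subject whose score falls below 5 "prior to receipt of study drug he/she will be termed an 'Early Responder' and will not be included in the study". Such subjects are replaced. Once any study drug has been given, the subject counts as dosed, is followed to the end (Protocol 4.4.4 and 6.3.1.3) and belongs to the ITT set (Protocol 8.1.1 and 8.1.2).

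Dose 1 has its own clock. Protocol 5.4 places it "30 to 120 minutes after tPA has completed or mechanical thrombectomy begins (arterial puncture), whichever is sooner". Protocol 6.3.2.1.2 and SAP section 1 agree.

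**The concern.** The recheck for combination subjects is tied to one event (draping), and Dose 1 can be tied to another (the end of tPA). Nothing in either document orders the two. When tPA finishes well before the patient is draped, a site that follows every instruction can give Dose 1 before the recheck is due. The instruction to withhold drug then has nothing to act on.

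What is at stake is who belongs to the trial. A tPA-only subject who improves to NIHSS below 5 before Dose 1 is meant to be caught immediately before the infusion and replaced. A combination subject with the same course can receive study drug against the plan's own rule and stay in the ITT set. If that subject is on active drug and either receives two or more doses or has a confirmed DLT, the subject also informs the CRM (SAP 6.1).

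**Working it through.** The plan gives no figure to reproduce. The question is whether the order can reverse within the plan's own time limits.

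**Inputs, in minutes from onset**
- tPA start S, at most 270 (within 4.5 h, Protocol 2.3.2).
- tPA end T = S + 60 (60-minute administration in the tPA model, Protocol 5.5.1).
- Arterial puncture P < 360 (inclusion criterion 8, Protocol 4.1).
- Dose 1 window from A + 30 to A + 120, where A = min(T, P) (Protocol 5.4).
- Recheck R = P − g, where g is the time from draping to puncture. The documents do not give g; I assume 5, 15 or 30 minutes.

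**Case 1: puncture at or before the end of tPA (P ≤ T).** Then A = P and R = P − g, which is always before P + 30. The recheck comes first, by between 30 + g and 120 + g minutes.

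**Case 2: tPA ends first (T < P).** Then A = T.
- The recheck can follow Dose 1 if R > T + 30, that is, if draping is more than 30 minutes after tPA ends.
- The recheck follows the whole window if R > T + 120, that is, if draping is more than 120 minutes after tPA ends.

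**Worked example.** With S = 90 (1.5 h), T = 150 (2.5 h), and the Dose 1 window is 180 to 270 (3.0 to 4.5 h). With g = 15:
- a recheck after Dose 1 is possible for any puncture later than 150 + 30 + 15 = 195;
- the recheck falls after the whole window for any puncture later than 150 + 120 + 15 = 285;
- with puncture just under 360, draping is just under 345, which is up to 345 − 180 = 165 minutes after the earliest permitted dose and 345 − 270 = 75 minutes after the latest.

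**How wide the affected range is.** In whole minutes the latest puncture is 359. The first condition becomes 359 − g > S + 90, so S ≤ 268 − g. The second becomes 359 − g > S + 180, so S ≤ 178 − g.

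| Assumed g (min) | Latest tPA start at which the recheck can follow Dose 1 | Latest tPA start at which it can follow the whole window |
|---|---|---|
| 5 | 263 | 173 |
| 15 | 253 | 163 |
| 30 | 238 | 148 |

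The reversal is therefore possible, given a late enough puncture, for most of the 270-minute tPA window. No protocol deviation is needed. These are limits of possibility and say nothing about how often it happens.

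**The case against.** **The intent is clear.** Section 6.3.1.3 says that the recheck exists because the score may fall before the first dose, and its instruction to withhold drug assumes that the recheck comes first. The Early Responder definition covers any score below 5 before study drug, not only the scheduled recheck. A site that notices the recovery can therefore still act. This stands, but it does not require anyone to look before Dose 1 in this subgroup.

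**A pre-dose NIHSS is already scheduled.** Protocol 6.1 and 6.2 mark one before Dose 1 for everyone. The randomization score can satisfy that entry, and the recheck was added because that score can go out of date.

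**The tPA-only rule might apply.** A site could treat a patient who has so far had only tPA as tPA-only when Dose 1 falls due. The second rule looks forward to planned thrombectomy and points the other way. The Manual of Operations, cited in 6.3.1.3, may settle this but is not among the documents.

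**Stronger readings that the documents do not support**
- A reader might infer that any dosed subject enters the CRM. SAP 6.1 requires two or more doses or a confirmed DLT, and placebo subjects do not inform the model. Protocol 4.3.2 also allows study drug to be stopped in a subject who becomes ineligible. One dose without a DLT stays outside the CRM.
- A reader might infer that only combination subjects can be dosed after recovering. Thrombectomy-only subjects are also examined before draping and dosed at least 30 minutes after puncture, so they too can improve in between. What is particular to combination subjects is that the recheck itself can come after Dose 1.
- A reader might apply the 30- and 120-minute limits to puncture. They apply to draping, which comes earlier.
- A reader might infer bias between arms. Assignment is randomized and blinded at the site, and the recheck rule does not depend on arm.

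**Conclusion.** The concern holds in a limited form. For subjects who are to have thrombectomy in addition to tPA, both documents allow the eligibility recheck to fall after Dose 1, and the rule it serves then fails. For a recovered subject to be dosed through this gap, four things must coincide: tPA finishes first, draping is more than 30 minutes later, Dose 1 is given before draping, and the score has fallen below 5 by the time of Dose 1. Such subjects can be dosed; the documents do not show that they are. They give no rate for any of the four conditions, so any percentage would be a guess.

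The effect is probably small. Those affected met the NIHSS entry criterion at randomization, and subjects draped before or soon after the end of tPA are rechecked in time. The possibility rests on the documents' own time limits. Only the exact thresholds in the table depend on the assumed 5 to 30 minutes between draping and puncture.

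**What to change.** Reconcile Protocol 6.3.1.3 and SAP section 4 with the Dose 1 timing in Protocol 5.4 and 6.3.2.1.2 and SAP section 1, so that the repeat NIHSS cannot fall after Dose 1. One wording that would do this is to time it, for all thrombectomy subjects, just before draping or just before Dose 1, whichever is earlier. The choice of rule is the sponsor's.

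Leave the Early Responder definition as it is (any score below 5 before study drug). Tying it to this one examination would narrow it, because a subject seen to improve after draping but before Dose 1 would no longer qualify.

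The cost is one sentence in each document, with no added examination and no change to the dose or the dosing window. The change does not bring the recheck closer to Dose 1 when draping comes first. In Case 1 the gap of 30 to 120 minutes plus the drape-to-puncture time remains, and the sponsor should say whether that is acceptable.

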6.3.2 On-Study Evaluations/procedures

6.3.2.1.1 Study-Specific Baseline Procedures

Once a subject has been randomized into the study, the following will be performed prior to receipt of the investigational treatment:

- Chemistry (liver function, if not obtained during SOC pre-tPA work-up)
- Blood for serum antibody sample ('pre-dose')
- 'Pre-dose' vital signs (blood pressure, heart rate, temperature, respiratory rate, oxygen saturation)

6.3.2.1.2 Study-Specific Post-Treatment Procedures

Investigational Dose #1:

The first investigational dose of study drug should be started 30 to 120 minutes following completion of tPA or initiation of mechanical thrombectomy (arterial puncture), whichever occurs sooner.

After administration of 100 mL of investigational treatment, the following should be performed:

• Vital signs (blood pressure, heart rate, temperature, respiratory rate, oxygen saturation) should be collected at end of infusion (EOI) and approximately every hour (+/- 30 minutes) for 4 hours, then per local SOC. Temperature at EOI is not required.

NOTE: the NINDS tPA protocol should guide vital sign collection following tPA administration; therefore, actual collection may be more frequent than what will be captured for this study protocol. The eCRF will capture one hourly time point for the first 24 hours. For subjects who undergo mechanical thrombectomy only, one hourly time point for the first 24 hours must be captured.

- Blood for coagulation (PT, aPTT, INR, fibrinogen) should be collected 1 hour after EOI (+/-15 minutes).
- One post-dose ECG should be collected at EOI (C_{max}) (+ 5 minutes). The Investigator can decide which dose, 1-5, can be used for ECG collection. Since the ECG collection is flexible, it should be planned well in advance so that it is collected as close to EOI as possible. Should the ECG window be missed, it is preferred to defer the collection to the next planned investigational dose.

Investigational Doses #2-5:

Subjects should receive 100 mL of investigational treatment every 12 hours (+/- 1 hour) for up to 5 total doses (refer to section 5.4). Subjects will only receive investigational treatment for as long as they remain as an inpatient. The following should be performed:

- Vital signs should be collected just prior to infusion, at EOI and approximately every hour (+/- 30 minutes) for 4 hours, then per local SOC
- Blood for coagulation (PT, aPTT, INR, fibrinogen) should be collected from the arm opposite the infusion:
 - Prior to each infusion (within 60 minutes of infusion)

- 1 hour after EOI (+/- 15 minutes)
- If not collected previously, one post-dose ECG should be collected at EOI (C_{max}) (+ 5 minutes). The Investigator can decide which dose, 1-5, can be used for ECG collection. Since the ECG collection is flexible, it should be planned well in advance so that it is collected as close to EOI as possible. Should the ECG window be missed, it is preferred to defer the collection to the next planned investigational dose.

Investigational Dose #2-5 - Pharmacokinetics (performed at a sub-set of sites):

Blood for plasma PK samples must be collected from the arm opposite the infusion:

- EOI ("post-dose: 0")
- 20 minutes after EOI ("post-dose: 20m")
- 40 minutes after EOI ("post-dose: 40m")
- 60 minutes after EOI ("post-dose: 60m")
- 80 minutes after EOI ("post-dose: 80m")

The Investigator can decide which dose, 2-5, will be used for PK collection. **PK samples should** only be collected following one dose of study drug.

